## **Study Protocol and Statistical Analysis Plan**

**Title: Digital Clinical Hypnosis for Chronic Pain Management**

**NCT number: NCT06050083**

**Document date: 08/21/2025**

## Study Protocol

### Overview of Study 1 and Study 2

This protocol describes two studies that are a part of this project. They use the same experimental design to evaluate the feasibility of the digital program. The primary difference is that first study (Study 1) recruits individuals with chronic low back pain and the second (Study 2) recruits individuals with general chronic pain (which includes individuals with chronic low back pain as well as individuals with chronic pain as a secondary condition to another health problem, such as spinal cord injury). Both studies aim to enroll 50 participants, which, given an estimated 20% dropout rate, would allow for complete data from at least 40 participants in each study.

Both studies use a 2-arm prospective randomized controlled trial design to evaluate the feasibility of the program (called *Rose*) over an 8-week period. Participants are randomly assigned to one of two groups: *Rose* access for a full 8 weeks (Access group) or *Rose* access for 4 weeks (Waitlist control group). The Waitlist group will not have access to *Rose* for the first 4 weeks of the study and then have access to *Rose* for the final 4 weeks. The 4-week assessment point is the primary study endpoint. Primary (feasibility) and secondary (clinical) outcomes using the *Rose* program and self-report measures using the Research Electronic Data Capture (REDCap) program, hosted by the University of Washington Institute of Translational Health Sciences (ITHS). Participants complete the self-report measures at three timepoints: baseline (before randomization), 4 weeks after randomization (primary endpoint), and 8 weeks after randomization.

### Measures

**Feasibility.** The studies has five primary feasibility outcome domains: (1) frequency of listening to a hypnosis session; (2) participant satisfaction with *Rose*; (3) interest in having continued access to *Rose* after study completion; (4) willingness to pay for that continued access; and (5) system usability. For each feasibility outcome, we have *a priori* specific criteria for determining if *Rose* was feasible.

**Frequency of access.** The *Rose* application tracks how frequently participants listened to a session. In this domain, we propose that *Rose* would be feasible if at least 50% of the Access participants who were offered access to *Rose* used it at least once/week. This criterion was selected as clinical hypnosis sessions are usually scheduled to occur once/week, making this frequency a standard for this treatment.

**Satisfaction with *Rose*.** We assess satisfaction with *Rose* at the 4-week timepoint (i.e. 4-weeks after randomization) using a 5-point global treatment satisfaction scale ("Taking all things into account, how satisfied are you with using the *Rose* web application?"), whose response options ranged from 1 ("Very satisfied") to 5 ("Very dissatisfied"), or "Prefer not to Answer." We determined that *Rose* would be feasible if  $\geq$  50% of the participants who listened to at least one *Rose* session would rate being either "Somewhat satisfied" or "Very satisfied" with *Rose*.

**Interest in continued *Rose* access.** We assess interest in continued access to *Rose* by asking, that if the program were available, "... how interested would you be in downloading and using this application?" Participants respond to this question using a 5-point Likert scale ranging from 0 = "I would not be interested" to 5 = "I would be extremely interested." We determined that *Rose* would be feasible if  $\geq$  50% of the

Access group participants who used *Rose* per protocol (i.e., at least 4 times during the four weeks after randomization) rated themselves as being at least "... a little interested" in using *Rose*.

**Willingness to pay for access to *Rose*.** We also assess participants' willingness to pay for continued *Rose* access after finishing the study. However, after the study began, we discovered that the question had been phrased incorrectly. The error was corrected when the error was discovered, but most of the Study 1 participants and four of the Study 2 had responded to the incorrectly worded question when the question was corrected. We therefore present the findings for this question only for the Study 2 participants in the Study 2 participants in the Access group who used *Rose* per protocol. We determined *a priori* that *Rose* would be feasible if  $\geq 40\%$  of the Access group participants who used *Rose* per protocol endorsed a willingness to pay for continued access.

**Usability.** Finally, we assess the usability of *Rose* using the System Usability Scale (SUS)(Lewis, 2018), a common 10-item measure of the overall usability of applications (sample item, "I thought the product was easy to use"). The cutoff we selected as the minimum average needed to determine that *Rose* was feasible was a score of  $\geq 68$ , which is the average SUS score across a large variety of software products (i.e., if *Rose*'s SUS score is  $\geq 68$ , it has an above average level of usability; (Banger, Kortum, & Miller, 2008)).

**Secondary outcomes: Changes in clinical domains.** Study 1 and Study 2 were both feasibility studies and are therefore not powered to detect statistically significant effects on any clinical outcome. However, the primary purpose of *Rose* is to improve pain-related quality of life domains for individuals who access and listen to *Rose*'s sessions, and these two feasibility studies were designed to provide data which could be used to inform a full clinical trial, if *Rose* is found to be feasible. A secondary aim of the two feasibility studies was therefore to provide preliminary estimates of the effects of *Rose* on a number of pain-related clinical outcomes to: (1) determine if anticipated improvements in these outcomes could be observed and, if so, to help (2) identify (a) the outcome domains that should be assessed in a fully-powered clinical trial, and (b) the measures that should be used to assess those domains in such a clinical trial.

We assess six clinical outcome domains: (1) immediate (i.e., pre- to post-session) changes in pain intensity; (2) change in average pain intensity from baseline (i.e., at randomization) to four weeks after randomization (primary endpoint) and to eight weeks after randomization (secondary endpoint); (3) change in pain interference from baseline to 4-weeks and from baseline to 8-weeks; (4) change in anxiety from baseline to 4-weeks and baseline to 8-weeks; (5) change in sleep disturbance from baseline to 4-weeks and baseline to 8-weeks; and (6) change in opioid use from baseline to 4-weeks and baseline to 8-weeks after randomization.

We measure pain intensity for the first two clinical outcomes using a 0-10 Numerical Rating Scales (NRS) of pain intensity. The endpoints of the NRSs used here were 0 = "No pain" and 10 = "Pain as bad as you can imagine." NRSs have a great deal of evidence supporting their reliability and validity as measures of pain intensity (Jensen, 2018) and are recommended over other ratings scale in pain clinical trials (Dworkin et al., 2005). To assess immediate changes in pain intensity associated with

listening to a *Rose* session, the *Rose* application prompts participants with a screen/question asking participants to rate their *current pain* on the 0-10 NRS just before and just after each listening session that included hypnotic suggestions for comfort. To assess change in average pain intensity from baseline to the 4-week and the 8-week assessment points, participants are asked to rate their "Average pain intensity in the past week" with the NRS at baseline (immediately after randomization), and then 4- and 8-weeks after randomization.

Pain interference, anxiety, and sleep disturbance at baseline, week 4, and week 8 are assessed by administering the Patient Reported Outcomes Measurement Information System (PROMIS) 8-item short form scales assessing these domains (PROMIS, 2024). PROMIS measures ask respondents to consider the magnitude or frequency of each symptom in the past seven days listed on the short forms using 5-point Likert scales with the response options responses varying as a function of the item (e.g., for magnitude, "Not at all" to "Very much"; for frequency, "Never" to "Always"). Responses are summed and then transformed to T-scores with a mean of 50 and a SD of 10 in the normative samples. All PROMIS measures are scored such that higher scores indicate higher levels of the domain being assessed (i.e., here, more pain interference, anxiety, or sleep disturbance). Evidence supports the validity and reliability of each of these measures in a variety of clinical populations, including individuals with chronic pain (Bhandari et al., 2022; Chimenti et al., 2021). The baseline internal consistencies (Cronbach's alphas) for these measures were: .95, .95, and .90 for Study 1 and .93, .86, .91 for Study 2 the PROMIS Pain Interference (8-item Short Form), PROMIS Anxiety (8-item Short Form), and PROMIS Sleep Disturbance (8-item Short Form) scales, respectively.

Opioid use is assessed by a self-report question asking participants if they are taking any opioid medications (with opioid examples listed, such as oxycodone, hydrocodone, and fentanyl). If the participant responded "Yes," a sub-question appeared asking for: medication name, dosage, and frequency of use in the past seven days. These participant responses were then converted to Morphine Milligram Equivalents (MME), which refers to "the amount of morphine that an opioid dose is equal to when [the opioid is] prescribed." MME converts different opioid medication dosages into a single unit and is calculated by comparing the results from two publicly available MME calculators (Hudson et al., 2018).

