### Statistical Analysis Plan

**Descriptive analyses of *Rose* use.** We will compute the total number and percent of times sessions of each different duration were listened to (i.e., 5, 10, or 20 minutes) and the number of percent that each different voice were listened to across the entire study period for both groups.

**Feasibility analyses.** To evaluate the feasibility of *Rose*, and for both studies, we will first compute the mean, standard deviation, median and range for the number of times participants in the Access conditions listened to sessions as well as the number and percent of the participants who listened to a session at least four times during the first four weeks of access (i.e., per protocol). To evaluate satisfaction with use of *Rose*, we will compute the average satisfaction rating for those participants in the Access groups who listened to at least one session during the first four weeks of access, as well as the number and percent of the responses to each of the satisfaction response options. To evaluate interest in continued access to *Rose*, we will compute the average of the interest ratings of the participants in the Access groups who used *Rose* per protocol (i.e., at least four times during from baseline to the 4-week assessment point), as well as the number and percent of the responses to each of the interest question response options. To understand the participants' willingness to pay for continued access to *Rose*, we will compute the number and percent of responses to each of the payment question response options for the Access group participants in each study who had used *Rose* per protocol. Given the inherent differences between the two studies, Fisher's exact tests will be used to compare satisfaction and interest for continued access between the two studies. To assess the usability of *Rose*, we will compute the average SUS for participants in the Access groups of each study who had used at least once.

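### Interest and willingness to pay are judged only among regular users, so both criteria can pass with as few as 28% and 24% of those offered access in favour, a floor under stated assumptions.

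*Combined protocol and SAP*

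**What the plan says.** The Measures section sets five feasibility domains, each with its own pass criterion, and uses three different denominators.

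- **Everyone offered access.** Frequency passes if "at least 50% of the Access participants who were offered access to" the program used it at least weekly.
- **Used at least once.** Satisfaction is judged among those who listened to at least one session. The Statistical Analysis Plan section averages usability over those who used the program at least once.
- **Regular users only.** Interest passes if at least 50% of the Access participants who used the program "per protocol (i.e., at least 4 times during the four weeks after randomization) rated themselves as being at least" a little interested. Willingness to pay passes if at least 40% of the Access participants who used it "per protocol endorsed a willingness to pay for continued access".

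The Statistical Analysis Plan section keeps the narrow denominator. For interest, "we will compute the average of the interest ratings of the participants in the Access groups who used" the program per protocol, with the number and percent for each response option. For payment, it plans the "number and percent of responses to each of the payment question response options for the Access group participants in each study who had used" the program per protocol. It also reports the number and percent "who listened to a session at least four times during the first four weeks of access (i.e., per protocol"). It plans no summary of either item over all Access participants, and no reason is given for the narrower denominator.

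The Measures section adds that the payment question was first worded incorrectly. Most Study 1 participants and four Study 2 participants had answered that wording, so the finding is presented for Study 2 only.

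**The concern.** Using a self-directed program four times in four weeks is a choice made after randomization, and it is likely to go with wanting the program. Someone who listened one to three times and stopped can still say whether they want continued access, yet is not counted on that question. The Statistical Analysis Plan section recognises this kind of link elsewhere. In the analysis of pre- to post-session pain change, it allows that people who benefit more may listen more, and it plans a sensitivity analysis. No such check is planned for interest or payment, which are primary feasibility domains.

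Each criterion, when met, leads to the statement that the program is feasible, with no qualifier about regular users. The studies are meant to inform a full trial, which would offer the program to people before anyone knows who will use it regularly. A high percentage among regular users does not by itself describe that population.

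**Working it through.** **The plan's own arithmetic.** The only sample-size figure is 50 enrolled per study, to leave 40 with complete data at 20% dropout: 50 × (1 − 0.20) = 40. It reproduces. The documents give no figure for interest or payment among all those offered access.

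**Inputs.** Thresholds from the Measures section: frequency 50% of those offered, interest 50% of regular users, payment 40% of regular users. Access arm: 25, assuming 1:1 allocation of 50; a range of 20 to 30 is shown because the ratio is not stated. Weekly use and four uses in four weeks are not the same rule. Anyone who listens in each of the four weeks has at least four uses, so setting the two counts equal gives the smallest number of regular users compatible with passing frequency.

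**Direction.** Let u be the share of regular users, p the interest among them and q the interest among the rest.

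- All-offered share = u·p + (1 − u)·q.
- Excess of the per-protocol figure = p − [u·p + (1 − u)·q] = (1 − u)(p − q).

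The excess is positive whenever regular users are more interested than the others, and zero if they are equally interested. Two illustrations with u = 0.5 and assumed p and q:

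- p = 70%, q = 10%: the criterion reads 70%; all-offered 0.5 × 0.70 + 0.5 × 0.10 = 40%. The two figures fall on opposite sides of 50%.
- p = 80%, q = 30%: the criterion reads 80%; all-offered 0.5 × 0.80 + 0.5 × 0.30 = 55%. Both pass.

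**Floor in whole persons, 25 in the Access arm, q = 0.**

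- Frequency just met: 0.50 × 25 = 12.5, so 13 users (52%).
- Interest just met: 0.50 × 13 = 6.5, so 7/13 = 54%. Over all offered: 7/25 = 28% (exact 95% CI 12% to 49%).
- Payment just met: 0.40 × 13 = 5.2, so 6/13 = 46% (5/13 = 38% fails). Over all offered: 6/25 = 24% (exact 95% CI 9% to 45%).

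For an Access arm of 20 to 30, the same steps give floors of 25% to 29% for interest (for example 5/20 and 6/21) and 20% to 24% for payment (for example 4/20 and 6/25).

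**What the planned output leaves open.** Hold the regular users' answers at 7/13 and 6/13 and vary the share of the other 12 in favour:

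| Share of the other 12 in favour | Interested, of 25 | Willing to pay, of 25 |
|---|---|---|
| none | 7 (28%) | 6 (24%) |
| one quarter (3) | 10 (40%) | 9 (36%) |
| half (6) | 13 (52%) | 12 (48%) |
| all (12) | 19 (76%) | 18 (72%) |

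All four rows would produce the same planned tables. On the all-offered denominator, the same thresholds would need 13/25 interested and 10/25 willing to pay, so the first two rows would fall short on both items.

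**The case against.** The denominators are openly stated and described as a priori. Asking regular users about *continued* access is a defensible conditional question. The Measures section describes the program's purpose in terms of people who access and listen to it, uptake is tested separately by the frequency criterion, and there is no combined rule across domains. People who tried the program and stopped still count for satisfaction and usability. All of this stands. It is why the criteria should be kept, but it does not support an unqualified feasibility statement on these two items.

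A reader might infer that only about a quarter of those offered access would want the program. The documents do not support that. The figure needs every criterion to be only just met and no one among the other 12 to be even a little interested, which is a low bar. It also sits uneasily with the selection argument: if regular use expresses interest, 7 of 13 is a low count among regular users. With 9/13 regular users and 4/12 others interested, the share is 13/25 (52%), and interest passes on both denominators.

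A reader might also infer that the selection is hidden. It is not. The count of regular users and their answers by response option are both planned, so 7/25 can be rebuilt. Only the lighter users' answers are missing.

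Counting non-response as a negative answer brings the opposite bias. At the planned 20% dropout that is 0.20 × 25 = 5 people. This stands, so that version is a bound and needs a respondents-only figure beside it.

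**Conclusion.** The point holds in a limited form. Interest and willingness to pay are measured in a group selected by behaviour that probably tracks interest, so the percentages probably overstate interest among all those offered access. The size of the overstatement cannot be known from the planned output. Under 25 in the Access arm and frequency only just met, passing results are compatible with as few as 28% interested and 24% willing to pay. The same planned tables are also compatible with 76% and 72%. The low end rests on zero interest or willingness among the other 12 and is not an expected value.

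The payment part applies to Study 2 only. It would be wrong to read it as a result for both studies, or to assume valid answers from all 25, given the incorrectly worded question.

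The analysis is valid for regular users. What a pass does not support on its own is a statement about everyone offered the program. This is worth correcting in the plan, but it does not invalidate the studies.

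**What to change.** Keep the a priori per-protocol criteria and their thresholds. Add to the Statistical Analysis Plan section:

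1. **Interest.** For each study, also report the number and percent at least a little interested among all Access participants offered access, in two versions: non-response counted as not interested, and respondents only.
2. **Willingness to pay.** Report the same two versions for Study 2 Access participants, leaving out those who answered the incorrect wording and stating how many were left out. The Measures section does not say how many of the four were in the Access arm or whether they are excluded from the per-protocol figure, so state both. Align the analysis text, which plans this item for each study, with the Study 2 restriction in the Measures section.
3. **Wording.** Where only the per-protocol figure meets the threshold, conclude 'feasible among regular users'.

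The cost is a few sentences and two small tables. As described, neither question is put only to regular users, so no new data should be needed. The downside is a less favourable companion figure, and the version that counts non-response as negative is a conservative bound and should be labelled so.

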## Procedures

### Consent and enrollment

**Study 1 (Chronic Low Back Pain).** The Study 1 participants are recruited using Research Match, a national research participant registry managed by the National Institute of Health. We use a multi-step recruitment process to identify eligible participants and focus on recruiting a racially diverse sample. First, we set the Research Match location filters to be anywhere in the United States, health condition filters to "Chronic Low Back Pain," demographic filters to any sex/gender, and race/ethnicity filters to all non-White or Hispanic/Latinx individuals. After screening and enrolling participants from this first recruitment wave, we evaluate how close we were to our recruitment goals for sex and race. Our goal is to have racial diversity that is at or above average racial diversity percentages for the Seattle metropolitan area. That is:  $\leq 47\%$

White Non-Latino/Latina,  $\geq 11\%$  Asian,  $\geq 6\%$  Black or African American, and  $\geq 10\%$  More than one Race, and self-identified ethnicity (goal:  $\geq 6\%$  Hispanic or Latinx). Next, we adjust the Research Match filters to include White/Caucasian, Non-Hispanic Latinx adults until we reached our recruitment goal of  $N = 50$ . Potentially eligible participants received a study email invitation from Research Match with a link to our online REDCap screening form. The online screening form provided a UW Institutional Review Board (IRB) approved study summary and collected participants' contact information and screening question responses.

The Study 1 screening form assesses for all study inclusion and exclusion criteria except for exclusion criteria (1), (2), and (3), which are assessed via telephone interview later. The inclusion criteria include: (1) 18 years old or older; (2) self-reported chronic low back pain (i.e., pain in the low back that has been ongoing for 3 months or more; and occurs on at least half the days in the past 3 months); (3) average pain intensity in the past week of  $\geq 4$  on a 0-10 scale, where 0 = "No Pain" and 10 = "Pain as bad as you can imagine"; (4) reads, speaks, and understands English; (5) regular access to the internet per self-report; and (6) access to a device (smartphone, desktop, laptop, tablet, etc.) that can connect to the internet. The study exclusion criteria include: (1) history or current diagnosis of primary psychotic or major thought disorder (i.e. Schizophrenia, Psychosis, Bipolar Disorder) with current active symptoms such as active delusional or psychotic thinking (self-report) within the past 5 years per self-report; (2) psychiatric hospitalization within the past 6 months per self-report; (3) psychiatric or behavioral conditions, including active suicidal ideation or intent to harm oneself or others, in which symptoms were unstable or severe within the past 6 months as disclosed during self-report screening; (4) active malignancy (e.g., cancer not in remission) or actively in cancer treatment per self-report; (5) planned surgery in the next six months that is related to the back pain per self-report; and (6) currently receiving or have received hypnosis treatment for any pain condition per self-report.

Potential participants who met the inclusion and exclusion criteria based on the REDCap screening form are contacted by study staff via telephone within 2 days of staff receiving a REDCap notification of a completed online screening form. During the phone call, study staff administer questions to assess the potential participant's history or current diagnosis of primary psychotic or major thought disorder, whether they had been hospitalized for a psychiatric treatment within the past 6 months, and the presence of active suicidal ideation or intent to harm oneself or others. Participants that endorse a history of being diagnosed with schizophrenia, psychosis or bipolar disorder but did not have any active symptoms were still eligible. Participants that endorse active suicidal ideation or any of the above nine follow up questions regarding symptoms that could interfere with participation (e.g., delusional thinking) were referred to the study PI ([name]), who is a licensed clinical psychologist, for a final eligibility decision (and potential referral to clinical resources).

**Study 2 (any type of chronic pain).** The recruitment process for Study 2 is almost identical to Study 1. The only difference is that instead of requiring that the participant have chronic low back pain, the Study 2 participants need to endorse having any type of chronic pain.

**Informed Consent.** For both Study 1 and Study 2, participants provide verbal informed consent over the telephone with study staff. The UW IRB approved a waiver of written informed consent for this study.

